4. STUDY DESIGN AND OUTCOMES

4.1. Trial Design and Rationale

The primary trial hypothesis is that pain coping skills training will improve pain and opioid use outcomes more than usual clinical care. The design is a multicenter, sequential, multiple assignment trial with a randomized component (Phase 1) and a non-randomized component (Phase 2). In Phase 1 (Weeks 1 - 24), participants will be randomized into one of two treatment groups: 1. Pain Coping Skills Training (PCST) for 24 weeks, or 2. Usual Care. The PCST intervention has two sequential components each taking place over 12 weeks: 1) weekly telehealth sessions with a PCST coach, and 2) daily interactive voice response (IVR) sessions via telephone. The primary outcome of pain interference will be ascertained at Week 12 which coincides with the end of the PCST weekly coaching sessions. In Phase 2, beginning at Week 24, participants in both randomized groups will be assessed for eligibility for a second intervention, buprenorphine, as an alternative to full agonist opioid pain medication. The main eligibility criterion for the buprenorphine intervention is current use of prescribed opioids at an average dose of \geq 20 morphine milligram equivalents (MME)/day. Participants who meet the buprenorphine eligibility criteria will be encouraged, but not required, to switch from their current opioid medication to buprenorphine to explore buprenorphine as an approach to addressing physical opioid dependence in patients receiving maintenance hemodialysis. Participants who do not meet the buprenorphine eligibility criteria will not be offered buprenorphine. All participants will continue to be followed from Week 24 until Week 36 (Phase 2) for ascertainment of pain, opioid use, and other outcomes to address durability of the effects of PCST, and, for those who switched to buprenorphine, to assess buprenorphine acceptability, tolerability, and efficacy as exploratory outcomes.

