To answer this question, the aforementioned linear mixed effects model is revised by adding the BPI Interference score at 24 weeks to the dependent variable. The linear mixed effects model is expressed as

$$y_{ijk} = \beta'_0 + \beta'_1 X_{ij} + \beta'_2 I(T_{ijk} = 12) + \beta'_3 I(T_{ijk} = 24) + \beta'_4 X_{ij} I(T_{ijk} = 12) + \beta'_5 X_{ij} I(T_{ijk} = 24) + \gamma'^T \mathbf{W}_{ij} + \theta'_i + \alpha'_{ij} + \varepsilon'_{ijk},$$

where y_{ijk} is the BPI Interference score for participant ij at time point k ($k = 1, 2, 3$) and $T_{ij3} = 24$. The estimand for **Question 2 in Table 10.1** is the contrast of PCST and Usual Care for the change at the 24-week time point; i.e., β'_5 . Differences in changes, their 95% confidence intervals, and p-values will be presented.

Question 3 (Table 10.1): Are the effects of PCST sustained?

To answer this question, the aforementioned linear mixed effects model is revised by adding the BPI Interference score at 36 weeks to the dependent variable. The linear mixed effects model is expressed as

$$y_{ijk} = \beta_0'' + \beta_1'' X_{ij} + \beta_2'' I(T_{ijk} = 12) + \beta_3'' I(T_{ijk} = 24) + \beta_4'' I(T_{ijk} = 36) + \beta_5'' X_{ij} I(T_{ijk} = 12) + \beta_6'' X_{ij} I(T_{ijk} = 24) + \beta_7'' X_{ij} I(T_{ijk} = 36) + \gamma''^T W_{ij} + \eta'' V_{ij} I(T_{ijk} \geq 24) + \delta'' Z_{ij} I(T_{ijk} \geq 24) + \theta_i'' + \alpha_{ij}'' + \varepsilon_{ijk}''$$

where y_{ijk} is the BPI Interference score for participant ij at time point k ($k = 1, 2, 3, 4$), $T_{ij4} = 36$, V_{ij} is the binary buprenorphine eligibility indicator ($V_{ij} = 1$ if buprenorphine eligible; $V_{ij} = 0$ if not buprenorphine eligible), Z_{ij} is the binary buprenorphine indicator ($Z_{ij} = 1$ if initiated buprenorphine; $Z_{ij} = 0$ if declined buprenorphine), and η'' and δ'' are regression parameters for the fixed effects. The estimand for **Question 3** in **Table 10.1** is the contrast of PCST and Usual Care for the change at the 36-week time point; i.e., β_7'' . Differences in changes, their 95% confidence intervals, and p-values will be presented.

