10.2.3.2 Analyses of the Secondary Endpoints

The secondary endpoints include pain severity, pain catastrophizing, opioid use, other PROs, hospitalizations, falls and mortality.

For continuous endpoints, such as pain severity, pain catastrophizing, and opioid use expressed as MME/day., similar methods as described for the primary outcome will be used to compare differences in changes of the endpoints between PCST and Usual Care at 12 (**Table 10.1; Question 1**), 24 (**Table 10.1; Question 2**), and 36 (**Table 10.1; Question 3**) weeks; i.e., linear mixed effects models with adjustment for baseline measures (and additional adjustment for buprenorphine eligibility and initiation of buprenorphine for **Question 3 in Table 10.1**), taking into account the repeated measures over time and clustering of recruitment sites via random effects.

For binary endpoints, such as the composite of pain interference and opioid use, generalized linear mixed effects models with a binomial distribution and a log link adjusting for baseline measures (additionally adjusting for buprenorphine eligibility and initiation of buprenorphine for **Question 3 in Table 10.1**), taking into account the repeated measures over time and clustering of recruitment sites via random effects, will be used to compare relative risks between PCST and Usual Care at 12 (**Table 10.1; Question 1**), 24 (**Table 10.1; Question 2**), and 36 (**Table 10.1; Question 3**) weeks.

For recurrent endpoints (counts) such as number of hospitalizations and falls, participants will be followed from baseline to 36 weeks, loss-to-follow-up, or death, whichever comes first. Generalized linear mixed effects models with a Poisson distribution, an offset of follow-up time and a log link adjusting for baseline measures (additionally adjusting for buprenorphine eligibility and initiation of buprenorphine for **Question 3 in Table 10.1**) will be used to compare event rates between PCST and Usual Care during the Phase 1 study period (**Table 10.1; Questions 1 – 3**). Repeated measures over time and clustering of recruitment sites will be taken into account via random effects.

For time to event endpoints such as mortality, participants will be followed from baseline to 36 weeks, loss-to-follow-up, or death, whichever comes first. Cox proportional hazards models will be used to compare risks of

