all-cause mortality between PCST and Usual Care (**Table 10.1; Questions 1 – 3**), with the end of the 36-week study period and loss-to-follow-up treated as censoring events in the models. For time to event endpoints such as the first hospitalization (or fall), participants will be followed from baseline to 36 weeks, loss-to-follow-up, death or the first admission to hospital (or fall), whichever comes first. Cause-specific hazards models or sub-distribution hazards models will be used to compare risks of the first hospitalization (or fall) between PCST and Usual Care (**Table 10.1; Questions 1 – 3**) where death is a semi-competing event, and the end of the 36-week study period and loss-to-follow-up are censoring events. All proportional hazards models will adjust for baseline measures, time-dependent buprenorphine eligibility, and time-dependent initiation of buprenorphine and take into account clustering of recruitment sites via random effects (i.e., proportional frailty models). The assumption of proportionality for all proportional hazards models will be examined using Schoenfeld residuals plots. If the assumption of proportionality is violated, models that incorporate stratification or time dependent covariate-effects will be considered.

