10.6. Populations for Analyses

For questions related to the Phase 1 intervention, analyses will use an intent-to-treat (ITT) approach, in which all available data on all randomized participants are included. Participants who discontinue an assigned intervention will be encouraged to remain in the trial to provide complete follow-up data and will be included in the ITT analysis. For participants with missing outcome ascertainment due to withdrawal or other reasons, data from earlier assessments will be used. For example, for the primary objective for Phase 1, if Week 12 outcome data are not available, baseline data will be used.

The characteristics at the time of randomization for those participants without complete follow-up will be examined; however, there will be limited statistical power to detect differences between participants with and without complete follow-up. To assess potential biases introduced by differential withdrawal among the intervention groups, comparisons of withdrawal rates and/or time to withdrawal will be performed as an ancillary analysis to the primary efficacy analysis.

Other populations that may be used in secondary analyses are defined as follows:

- As-treated population: Any participant randomized into the study regardless of whether they received study intervention. As-treated participants will be analyzed according to the study intervention actually received.

- All-treated population: Any participant randomized into the study that received at least some of the study intervention.
- Per-protocol population: Any participant who was appropriately randomized and was exposed to the protocol-dictated study intervention for $\geq 75\%$ of the planned duration and had the outcome assessments through Week 24.

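### The Week 36 comparisons of PCST with Usual Care are declared intent-to-treat but adjust for buprenorphine eligibility and initiation, both of which arise after randomisation

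*Combined protocol and SAP*

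**What the plan says.** For questions about the Phase 1 intervention, Section 10.6 states that "analyses will use an intent-to-treat (ITT) approach, in which all available data on all randomized participants are included".

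Question 3 in Section 10.2.2.1 asks whether PCST effects last to Week 36. Its estimand is the arm-by-Week-36 coefficient from a mixed model that also contains the terms "V_{ij} I(T_{ijk} \geq 24) + \delta'' Z_{ij} I(T_{ijk} \geq 24". Here V "is the binary buprenorphine eligibility indicator". Z equals 1 for participants who started buprenorphine and 0 "if declined buprenorphine".

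The section on secondary endpoints (numbered 10.2.3.2) carries this over. Continuous endpoints such as "pain severity, pain catastrophizing, and opioid use expressed as MME/day" get "additional adjustment for buprenorphine eligibility and initiation of buprenorphine" for Question 3, as do binary and count endpoints. For time-to-event endpoints: "All proportional hazards models will adjust for baseline measures, time-dependent buprenorphine eligibility, and time-dependent initiation of buprenorphine".

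The Question 1 and 2 mixed models (Weeks 12 and 24) contain neither V nor Z. The adverse event comparison in Section 10.4, which includes falls, uses baseline covariates only.

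**The concern.** Neither V nor Z is a baseline covariate. Section 6.2.2 determines eligibility at Week 24, chiefly by prescribed opioid use of at least 20 MME/day. By then the PCST arm has had motivational interviewing on opioid reduction (Section 6.1; Sessions 5-12 in Table 6.1). Section 4.1 says: "The primary trial hypothesis is that pain coping skills training will improve pain and opioid use outcomes more than usual clinical care". If that is right, V should differ by arm. Z is the participant's own choice among those eligible.

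Adjusting for a variable that treatment has moved can remove part of the treatment effect or create one. The exposure is greatest for MME/day, because V is largely a dichotomised Week 24 value of that outcome. A reader told that the analysis is intent-to-treat would take the Week 36 coefficient as the randomised effect.

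There are two further defects in how Z is written:

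- It acts from Week 24 onwards. But the Week 24 questionnaires come before Phase 2 (Section 7.4.4), no drug is given at the initial prescriber visit (Section 6.2.7.4), and Section 10.3.3 treats Week 24 as the Phase 2 baseline.
- It has no stated value for the majority who are never offered buprenorphine.

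**Working it through.** **1. Is there a version without V and Z?** The general approach (10.2.2), subgroup (10.2.2.2), missing data (10.2.2.3) and population (10.6) sections contain no Week 36 efficacy model that omits them.

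**2. The plan's own figures.** The plan gives no figure for the Week 36 contrast. The nearest yardstick is Table 10.2 for N = 640, ICC 0.02, SD 2.
- Design effect: 1 + 0.02 × [((12.48/22.88)² + 1) × 22.88 − 1] = 1.574.
- Effective n per arm: 320/1.574 × 0.8/1.173 = 138.7 (stated: about 139).
- Detectable difference: (1.960 + 1.282) × 2 × √(2/138.7) = 0.78, as stated.

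**3. How the shift arises.** Let pV and pZ be the proportions with V = 1 and Z = 1 in each arm, and let η and δ be the coefficients of V and Z. Then, closely:

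planned contrast = contrast without V and Z − η × (pV in PCST − pV in Usual Care) − δ × (pZ in PCST − pZ in Usual Care).

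If PCST leaves eligibility and initiation alone, both differences are zero and nothing moves. If PCST lowers eligibility and eligible participants have higher doses (η > 0), the V term adds a positive amount to the planned contrast. A true zero then looks like a dose increase.

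**4. Pain interference by hand.** Section 10.3 expects at least 40 eligible, and its tables run from 20 to 80. With 40/640 = 6.25% or 80/640 = 12.5% eligible, and PCST cutting this by a quarter to a half (assumed), the arm difference in V is 1.6 to 6.3 percentage points. A V coefficient of 1 BPI point shifts the contrast by 0.016 to 0.063. The standard error with 640 × 0.8 = 512 analysed, SD 2 and no clustering is 2 × √(2/256) = 0.18.

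**5. MME/day by simulation.** The planned four-visit random-intercept model was fitted with and without V and Z.
- From the documents: 300 of 640 using opioids; 20, 40 or 80 eligible; 25-75% of those initiating (Table 10.6).
- Assumed: log-normal dose (log SD 1.0, within-person 0.3); 10% of Usual Care and 25-40% of PCST opioid users stop by Week 24.
- There were 600,000 participants per scenario. Neither missing data nor site clustering was simulated.

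Planned contrast as a percentage of the contrast without V and Z, Week 36:

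| Eligible of 640 | Buprenorphine not recoded | Buprenorphine counted as 0 MME |
|---|---|---|
| 20 | 94-95% | 97-106% |
| 40 | 91-93% | 96-111% |
| 80 | 89-91% | 95-123% |

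- Not recoded, the contrast is 0.03-0.38 MME/day smaller, or 0.08-0.33 of one standard error at 512 analysed.
- With a 10-30% dose cut under PCST and equal stopping: 93-99% (not recoded) and 109-128% (counted as 0).
- If the excess stopping has fully reversed by Week 36 (true contrast 0, not recoded): +0.03 to +0.33 MME/day.
- With no PCST effect on dose: 0.000.

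A second, wider set of assumptions (within-person correlation of log dose 0.5-0.9, 15-40% of Usual Care opioid users eligible) gave 78-205%. The 205% case (−0.59 against −1.22 MME/day) has about 105 of 640 eligible, above the plan's range of 80.

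**6. Other endpoints.**
- Composite relative risk: 1.305 becomes 1.301 and 1.414 becomes 1.403 with 40 eligible; 1.297 and 1.391 with 80.
- BPI: at most 0.036 points in the first set of scenarios and about 0.06 in the wider set.
- Hazard ratio, planned over unadjusted: 0.997-1.012 (40 eligible) and 0.994-1.023 (80).
- Count models were not quantified.

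**7. Timing of Z.** Entering Z at Week 36 only, instead of from Week 24, moves the adjusted MME/day contrast by 0.06-0.43 with 40 eligible if buprenorphine counts as 0, and by at most 0.02 if not recoded. BPI moves by up to 0.027 (40 eligible) or 0.055 (80). Coding Z from Week 24 removes only about half of the drug effect, because one coefficient spans a visit before treatment and a visit after it.

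**The case against.** Section 10.6 defines intent-to-treat by who is included, and these models exclude nobody. The plan openly chooses to estimate the durability of PCST net of a second, non-randomised treatment, which is a legitimate question. Question 3 is labelled secondary in Table 10.1, the primary outcome is Week 12 BPI Interference, and MME/day has clean contrasts at Weeks 12 and 24. The shifts are small: a bias of 0.33 standard errors at a true null raises the two-sided error from 5% to Φ(−1.63) + Φ(−2.29) ≈ 6.3%. The sizes rest on assumed stopping rates and a raw-scale fit, although Section 10.2.2.1 foresees a log transformation. Eligibility also has pregnancy, substance use, liver, QT and allergy criteria, so V is not simply the Timeline Followback value cut at 20.

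Much of this stands. It limits the importance, rules out precise claims about size, and means V is only mainly a cut of the outcome. It does not remove the structural problem. Including everyone does not make the coefficient the randomised difference once V differs by arm. Nor does the written model isolate PCST well, since Z is applied to a score taken before any buprenorphine.

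**Conclusion.** The concern holds. Every planned Week 36 efficacy comparison of the arms, and every hazards model, conditions on variables that arise after randomisation, and no efficacy version without them is specified. This rests on the text alone and is firm.

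The size is less certain. For MME/day the planned fit can understate or overstate the randomised effect, typically by about a tenth and, under some assumptions, by a quarter or more. The direction depends on how PCST acts on dose and on whether buprenorphine counts towards MME/day, which the documents do not state. For BPI Interference, the composite and the hazard ratios the shift is very small, and essentially zero if PCST does not change eligibility; these endpoints belong in the change for consistency. The primary analysis and the sample size are unaffected. The change should be made, but the point does not threaten the trial's main conclusion.

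**What to change.** Specify the main Question 3 and time-to-event comparisons as intent-to-treat with baseline covariates only, omitting V and Z. Keep the V/Z-adjusted model as a labelled sensitivity analysis of PCST durability apart from buprenorphine. In the mixed model, enter Z at Week 36 only and set Z = 0 for anyone never offered buprenorphine. State in the same place how buprenorphine is handled when MME/day is computed, because both fits depend on it.

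The cost is SAP wording and one additional fit for each affected endpoint. No new data and no change to trial conduct are needed.

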10.2.3.2 Analyses of the Secondary Endpoints

The secondary endpoints include pain severity, pain catastrophizing, opioid use, other PROs, hospitalizations, falls and mortality.

For continuous endpoints, such as pain severity, pain catastrophizing, and opioid use expressed as MME/day., similar methods as described for the primary outcome will be used to compare differences in changes of the endpoints between PCST and Usual Care at 12 (**Table 10.1; Question 1**), 24 (**Table 10.1; Question 2**), and 36 (**Table 10.1; Question 3**) weeks; i.e., linear mixed effects models with adjustment for baseline measures (and additional adjustment for buprenorphine eligibility and initiation of buprenorphine for **Question 3 in Table 10.1**), taking into account the repeated measures over time and clustering of recruitment sites via random effects.

For binary endpoints, such as the composite of pain interference and opioid use, generalized linear mixed effects models with a binomial distribution and a log link adjusting for baseline measures (additionally adjusting for buprenorphine eligibility and initiation of buprenorphine for **Question 3 in Table 10.1**), taking into account the repeated measures over time and clustering of recruitment sites via random effects, will be used to compare relative risks between PCST and Usual Care at 12 (**Table 10.1; Question 1**), 24 (**Table 10.1; Question 2**), and 36 (**Table 10.1; Question 3**) weeks.

For recurrent endpoints (counts) such as number of hospitalizations and falls, participants will be followed from baseline to 36 weeks, loss-to-follow-up, or death, whichever comes first. Generalized linear mixed effects models with a Poisson distribution, an offset of follow-up time and a log link adjusting for baseline measures (additionally adjusting for buprenorphine eligibility and initiation of buprenorphine for **Question 3 in Table 10.1**) will be used to compare event rates between PCST and Usual Care during the Phase 1 study period (**Table 10.1; Questions 1 – 3**). Repeated measures over time and clustering of recruitment sites will be taken into account via random effects.

For time to event endpoints such as mortality, participants will be followed from baseline to 36 weeks, loss-to-follow-up, or death, whichever comes first. Cox proportional hazards models will be used to compare risks of

all-cause mortality between PCST and Usual Care (**Table 10.1; Questions 1 – 3**), with the end of the 36-week study period and loss-to-follow-up treated as censoring events in the models. For time to event endpoints such as the first hospitalization (or fall), participants will be followed from baseline to 36 weeks, loss-to-follow-up, death or the first admission to hospital (or fall), whichever comes first. Cause-specific hazards models or sub-distribution hazards models will be used to compare risks of the first hospitalization (or fall) between PCST and Usual Care (**Table 10.1; Questions 1 – 3**) where death is a semi-competing event, and the end of the 36-week study period and loss-to-follow-up are censoring events. All proportional hazards models will adjust for baseline measures, time-dependent buprenorphine eligibility, and time-dependent initiation of buprenorphine and take into account clustering of recruitment sites via random effects (i.e., proportional frailty models). The assumption of proportionality for all proportional hazards models will be examined using Schoenfeld residuals plots. If the assumption of proportionality is violated, models that incorporate stratification or time dependent covariate-effects will be considered.

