1. Does PCST consisting of weekly, live, coach-led sessions improve outcomes at 12 weeks? This is the primary trial question.	PCST vs Usual Care; baseline to Week 12	
 Primary: BPI Interference Secondary: pain severity, pain catastrophizing, opioid use, other PROs, and clinical outcomes 	
 Linear mixed effects models for continuous outcomes; Generalized linear mixed effects models for binary outcomes; Time to event models accounting for semi-competing risk of death (where relevant)
2. Does PCST consisting of weekly, live, coach-led sessions followed by IVR improve outcomes at 24 weeks? This is a secondary question and findings will be interpreted as such.	PCST vs Usual Care; baseline to Week 24	
 Primary: BPI Interference Secondary: pain severity, pain catastrophizing, opioid use, other PROs, and clinical outcomes 	
 Linear mixed effects models for continuous outcomes; Generalized linear mixed effects models for binary outcomes; Time to event models accounting for semi-competing risk of death (where relevant)
3. Are the effects of PCST sustained? This is a secondary question and findings will be interpreted as such.	PCST vs Usual Care; baseline to Week 36	
 Primary: BPI Interference Secondary: pain severity, pain catastrophizing, opioid use, other PROs, and clinical outcomes 	
 Linear mixed effects models for continuous outcomes; Generalized linear mixed effects models for binary outcomes; Time to event models accounting for semi-competing risk of death (where relevant)

Exploratory Questions Addressed with the Phase 2 Intervention

4. Is buprenorphine acceptable to patients?	Single group	
 % Initiating buprenorphine Reasons for non-initiation of buprenorphine 	Summary statistics: frequency, percentage
5. How well tolerated is buprenorphine?	Single group	
 % who do not discontinue buprenorphine due to adverse effects Adverse effects 	Summary statistics: frequency and percentage

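### The analyses of falls, hospitalizations and deaths do not use the Week 12, 24 and 36 horizons that Table 10.1 sets for Questions 1, 2 and 3; no window written for them fits Question 1

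*Combined protocol and SAP*

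**What the plan says.** Table 10.1 in Section 10.1 gives each randomized comparison its own horizon: "PCST vs Usual Care; baseline to Week 12" for Question 1, "PCST vs Usual Care; baseline to Week 24" for Question 2 and "PCST vs Usual Care; baseline to Week 36" for Question 3. The outcome list is the same in all three rows: "Secondary: pain severity, pain catastrophizing, opioid use, other PROs, and clinical outcomes". Clinical outcomes therefore belong to each question at that question's horizon.

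Section 10.2.3.2 carries this mapping through for continuous and binary endpoints, assigning 12, 24 and 36 weeks to Questions 1, 2 and 3. For clinical events it does not:

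- **Counts of hospitalizations and falls.** The follow-up sentence reads "participants will be followed from baseline to 36 weeks, loss-to-follow-up, or death, whichever comes first", and the Poisson model has a follow-up-time offset. The model is then to "compare event rates between PCST and Usual Care during the Phase 1 study period", tagged Questions 1 to 3. Section 4.1 fixes the length of that phase: "In Phase 1 (Weeks 1 - 24), participants will be randomized into one of two treatment groups".
- **Mortality.** The same 36-week follow-up applies, and the Cox models are specified "with the end of the 36-week study period and loss-to-follow-up treated as censoring events in the models", again for Questions 1 to 3.
- **First hospitalization or first fall.** Follow-up to 36 weeks and censoring at the end of that period, tagged to the same three questions.

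Buprenorphine terms are handled differently in the two model families. The count model adds them for Question 3 only; every proportional hazards model carries them as time-dependent covariates.

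**The concern.** Question 1 is the trial's primary question and concerns the 12-week coached period. An event analysis that runs on to Week 36 estimates something else: an average over coaching, the IVR booster and the buprenorphine phase. If the effect on events fades after coaching ends, that average is pulled toward no effect. Whether the effect lasts is what Question 3 asks, so the Question 1 analysis should not depend on the answer.

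For counts there is a second problem. Two windows are written a few lines apart, and the choice between them would fall to the analyst, possibly after the data have been seen. Falls, hospitalizations and deaths are named secondary outcomes that Section 4.2.2.3 expects the interventions to reduce, so their windows should be fixed in advance.

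**Working it through.** The plan states no event rate, event count or power for these comparisons, so there is no figure of its own to reproduce. The check compares the written windows and then sizes the mismatch.

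**1. Windows side by side (weeks from baseline)**

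| Source | Question 1 | Question 2 | Question 3 |
|---|---|---|---|
| Table 10.1 | 0–12 | 0–24 | 0–36 |
| Death; first hospitalization or fall (10.2.3.2) | 0–36 | 0–36 | 0–36 |
| Counts, follow-up sentence (10.2.3.2) | 0–36 | 0–36 | 0–36 |
| Counts, comparison sentence (10.2.3.2 with 4.1) | 0–24 | 0–24 | 0–24 |

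The hazards models match Table 10.1 for Question 3 only. For counts, the 36-week reading matches Question 3 only and the 24-week reading matches Question 2 only. No row below the first gives Question 1 its 12 weeks.

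**2. Share of person-time outside the horizon, assuming complete follow-up**

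- 36-week window, Question 1: (36 − 12)/36 = 67% falls after the horizon.
- 36-week window, Question 2: (36 − 24)/36 = 33% falls after the horizon.
- 24-week window, Question 1: (24 − 12)/24 = 50% falls after the horizon.
- 24-week window, Question 3: 12 of the 36 weeks, or 33%, are left out.

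**3. Effect on a rate ratio (illustration; the effect sizes and durations are assumptions)**

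Take a constant background rate and a rate ratio RR that acts until week E and equals 1 afterwards. Over a window of w weeks the expected rate ratio is [min(E, w) × RR + max(0, w − E)] / w.

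- RR 0.70, E = 12: over 12 weeks, 0.70; over 24 weeks, (12 × 0.70 + 12)/24 = 0.85; over 36 weeks, (12 × 0.70 + 24)/36 = 0.90.
- RR 0.70, E = 24: over 24 weeks, 0.70; over 36 weeks, (24 × 0.70 + 12)/36 = 0.80.
- RR 0.70, E = 36: 0.70 over every window, so no dilution.
- Range for E = 12 over 36 weeks: RR 0.6 gives (7.2 + 24)/36 = 0.87; RR 0.9 gives (10.8 + 24)/36 = 0.97.

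This arithmetic is for event rates. A hazard ratio averaged over 36 weeks would be diluted in the same direction, but not by exactly these amounts.

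**4. Event numbers (illustration)**

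Section 2.2.1 cites a yearly risk p of 25–30% for at least one fall. Assuming a constant hazard, 320 participants per arm (640/2) and no attrition, the expected number with a fall by week w is 320 × [1 − (1 − p)^(w/52)].

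| p | Week 12 | Week 24 | Week 36 |
|---|---|---|---|
| 25% | 20.6 | 39.8 | 57.8 |
| 30% | 25.3 | 48.6 | 70.0 |

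So 1 − 20.6/57.8 = 64% (and 1 − 25.3/70.0 = 64%) of the first falls in a 36-week analysis would come after Week 12.

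**The case against.** The strongest defence is that separate analyses per question were intended. Each event paragraph cites Table 10.1, which supplies the horizons, and the 36-week sentences could describe maximum follow-up. The count model adds buprenorphine terms for Question 3 only, which makes sense only if each question has its own model. It also allows for repeated measures over time, which suggests more than one record per participant. The Phase 1 label may be loose shorthand, since all of Section 10.2 is headed as concerning the Phase 1 randomization and yet covers Week 36.

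Much of this is plausible for counts, but the windows themselves are not written. For the hazards models the text is explicit: censoring is at the end of 36 weeks, and the rule is tagged to all three questions.

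The defence also rules out several stronger readings:

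- A reader might infer that Section 10.2.3.2 overrides Table 10.1. Nothing gives either place precedence; they conflict.
- A reader might infer that Question 2 is certainly answered with the wrong window for counts. On the 24-week reading its window is correct.
- A reader might infer that buprenorphine terms contaminate the Week 12 and Week 24 models. The count model already limits them to Question 3. In the hazards models they are time-dependent and zero before Week 24, when eligibility is first assessed, so removing them is only tidying.

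Finally, Section 6.1.5 has the IVR booster continue to Week 24 to maintain or improve gains, so an effect that stops at Week 12 is not the only plausible case. Schoenfeld residual plots are planned, with time-dependent effects to be considered if proportionality fails. That is a partial safeguard, but it does not define a 12-week or 24-week estimate.

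**Conclusion.** The concern holds as a conflict between Table 10.1 and the event analyses. It is clearest for death and first hospitalization or fall, where the stated censoring rule, applied literally, brings later events into Questions 1 and 2. For counts the text contradicts itself, and neither reading fits Question 1.

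The person-time shares (67% after Week 12 and 33% after Week 24) assume only complete 36-week follow-up. The size of any dilution is not known. It runs from none, if the effect is sustained, to 0.70 appearing as 0.90, if the effect stops at Week 12. The 0.90 should not be read as a predicted bias, because the documents give no effect size for these events.

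Only secondary endpoints are involved. The primary analysis and the target of 640 participants are unchanged.

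**What to change.** In Section 10.2.3.2, state one window per question for both the count and the hazards models. Event counting, the follow-up offset and administrative censoring should end at Week 12 for Question 1, Week 24 for Question 2 and Week 36 for Question 3. Replace the Phase 1 wording in the count paragraph with these windows. The time-dependent buprenorphine terms then drop out of the Question 1 and Question 2 hazards models; the count model needs no change on that point.

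The cost is wording plus some precision. Events are already ascertained every four weeks (Appendix 14.2), so no new data are needed. Questions 1 and 2 will have fewer events and wider intervals: on the illustration above, about 21 to 25 participants with a fall per arm at Week 12, against 58 to 70 at Week 36.
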